### **2.3.3 Pharmacokinetic population**

For PK analyses, the PK population is defined as all randomized and treated patients who contribute with at least 1 valid plasma concentration of SAR425899. The PK data will be analyzed according to the treatment actually received (see [Section 2.3.2](#)).

### **2.3.4 Pharmacodynamic population**

The analysis of pharmacodynamics biomarkers will be conducted on the ITT population. The data will be analyzed according to the treatment as randomized (see [Section 2.3.1](#)).

### **2.3.5 NASH and cardiovascular biomarkers population**

The analysis of NASH and cardiovascular biomarkers will be conducted on the ITT population. The data will be analyzed according to the treatment as randomized (see [Section 2.3.1](#)).

### **2.3.6 Patient-reported outcome population**

The analysis of PROs will be conducted on the ITT population. The PROs data will be analyzed according to the treatment as randomized (see [Section 2.3.1](#)).

### **2.3.7 Substudy population**

Patients included in a substudy (meal test, or holter monitor substudy) are defined as patients who signed the informed consent for the substudy, and have at least one post baseline measurement for any of the substudy variables.

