- ^a In case of rescue therapy, all assessments planned in V12 should be performed before starting rescue therapy, patients then continue the study treatment (including metformin), and all visits and assessments should be performed as scheduled. In case of premature permanent IMP discontinuation, patients should have a visit as soon as possible with the assessments normally planned in V12 (the standardized meal test and PK collections are performed only if the patient receives the IMP the day of the visit, note that otherwise predose PK sample can be taken if the patient receives the IMP the day before). Afterward, the patients should continue in the study up to the scheduled date of study completion. They should be followed up according to the study procedures as specified in the protocol (except for the 3 day safety post-treatment and PK assessment). If the patient drops out from the study at the time of IMP discontinuation regardless if the patient receives the IMP or not on the day of the meal test, the meal test should be performed. However, PK collections are performed only if the patient receives the IMP the day of the visit, otherwise predose PK sample can be taken if the patient receives the IMP the day before.
- ^b Weight will be recorded to the nearest 0.1 kg and should be measured using calibrated scales. The same pair of scales should preferably be used throughout the trial. Weight should be measured in the fasting state in the morning at approximately the same time with an empty bladder, without shoes and only wearing undergarments or light clothing. Weight measured at screening Visit 1 will be used only for calculation of screening BMI for eligibility criteria whereas weight measured at Visit 4 will be used as baseline for assessment of change in body weight and for calculation of baseline BMI which will be the BMI value used for stratification.

- c* At Visit 9, abbreviated/targeted physical examination only.
- d* Diary will be reviewed at each on site visit.
- e* Counseling will be provided at screening Visit 3 or Visit 4.
- f* Only for patients in SAR425899 or Placebo arms.
- g* First dose of IMP will be done on-site .IMP administration every day along the 26-weeks, but at each visit on site, the IMP administration will be done on site by the patient himself.
- h* 7-point profile to be conducted over a single 24-hour period in the week before Visit 4, Visit 10 and Visit 12.

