9.2.1.2.2 Standardized meal test definition and change in postprandial glucose

Patients will undergo a standardized meal challenge to assess PPG, insulin, proinsulin, C-peptide as well as excursion values for above parameters at Visit 3 (Week -1) and at the end of treatment (Visit 12, Week 26) ([Table 2](#)).

A standardized meal will be served 2 hours after morning dose (at T2H) on Visit 12 (Week 26), and at the corresponding time on Visit 3 (Week -1). The standardized meal for all patients should be consumed within a 10-minute period.

The standardized meal contains approximately 600 kcal and is composed of 50 to 55% carbohydrates, 15 to 20% proteins, and 25 to 30% fat. The composition and quantity of standardized meal must be identical throughout the study.

The start of the standardized meal is defined as a reference timepoint for further blood sample collection.

Blood samples for determination of plasma glucose, and insulin, proinsulin, C-peptide, in response to meal test will be collected at (premeal, 10 min, 20min, 0.5h, 1h, 1.5h, 2h, 3h, 4h postmeal) on Weeks -1 and 26. The excursions values for plasma glucose, and insulin, proinsulin, C-peptide will be calculated by subtracting the premeal values from the values collected for each respected timepoints at 10min, 20min, 0.5h, 1h, 1.5h, 2h, 3h and 4h. The AUC values for the above meal test parameters may be calculated as necessary.

Meal test ingestion time should be recorded in the eCRF.

Meal test will be proposed to all the population, and will be limited to the first up to 50% of patient who agree.

If the patient needs to receive a rescue antidiabetic medication, the standardized meal test should be performed before the introduction of the rescue medication and at the end of the study.

In case of permanent discontinuation of the treatment with IMP, the standardized meal test should be performed only if the patient receives the IMP on the day of the visit. The meal test should also be performed at the end of study as planned.

Table 2 - Sampling schedule for glucose, insulin, proinsulin and C peptide in response to a standardized meal test in up to 50% subset of all patients

Blood sampling time (hh:mm)	Blood sampling
Morning study treatment injection	00:00
Pre meal	X
Standardized meal	02:00
2h10 after morning injection	02:10
2h20 after morning injection	02:20
2h 30 after morning injection	02:30
3h00 after morning injection	03:00
3h30 after morning injection	03:30

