Patients treated but not randomized, randomized but not treated, patients randomized but not treated as randomized will be identified and described in separate listings. Patients of the second category (randomized and not treated) will be part of efficacy analyses. Patients of the third

category (randomized and not treated as randomized) will be part of efficacy and safety analyses (see [Section 2.3](#)). Safety data of patients treated but not randomized will be reported separately.

The randomization strata [HbA1c at screening ( $<8\%$ ,  $\geq 8\%$ ) and Visit 4 (Day 1) BMI ( $<35.0 \text{ kg/m}^2$ ,  $\geq 35.0 \text{ kg/m}^2$ )] assigned by IRT will be summarized. The percentages will be calculated using the number of randomized patients as the denominator. The discrepancy between the strata assigned by IRT and the information reported on eCRF will be listed for all randomized patients.

Kaplan-Meier (KM) plots of the cumulative incidence of IMP discontinuation due to any reason or due to AE will be provided for the 26-week treatment period. Additionally, a listing of these patients, along with the reason for treatment discontinuation, study completion status and the reason for study discontinuation, will be provided. Time to treatment discontinuation will be defined as the number of days from the first injection of IMP until the day of treatment discontinuation. All completers will be considered as censored observations. The censoring time will be the number of days from the first injection of IMP until the last injection date during 26-week treatment period.

All major or critical deviations including deviations related to randomization procedure will be listed and summarized in tables giving numbers and percentages of deviations by randomized treatment group.

Additionally, the analysis populations for efficacy, safety, PK, and each of the substudy defined in [Section 2.3](#) will be summarized in a table by number of patients on the randomized population:

- Efficacy population: modified intent-to-treat (ITT) population,
- Safety population.
- PK population.
- Substudies

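### SAP 2.3.7 admits meal-test patients only with a post-baseline value, which removes some dropouts whom the plan's own control-based imputation is meant to cover

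*SAP*

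**What the plan says.** **Who is in.** SAP 2.3.7 requires that patients signed the substudy consent "and have at least one post baseline measurement for any of the substudy variables". SAP 2.2 treats the substudy sets as analysis populations, to be tabulated with "the analysis populations for efficacy, safety, PK, and each of the substudy defined in" SAP 2.3.

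**When the test is done.** Protocol 9.2.1.2.2 schedules it "at Visit 3 (Week -1) and at the end of treatment (Visit 12, Week 26"), so there is one planned post-baseline test. Early tests can also occur:

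- For rescued patients, "the standardized meal test should be performed before the introduction of the rescue medication and at the end of the study".
- At permanent IMP discontinuation, Protocol 9.2.1.2.2 says "the standardized meal test should be performed only if the patient receives the IMP on the day of the visit", and adds: "The meal test should also be performed at the end of study as planned".
- Footnote a of the Protocol 1.2 flow chart adds a case that 9.2.1.2.2 lacks. It begins "If the patient drops out from the study at the time of IMP discontinuation" and calls for the test whether or not IMP was taken that day.

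**How missing values are handled.** SAP 2.4.4 puts efficacy analyses on ITT unless stated otherwise. SAP 2.4.4.2 applies ANCOVA with placebo control-based multiple imputation to all continuous secondary efficacy endpoints. Under SAP 2.1.3.2 these include meal-test glucose, insulin, proinsulin and C-peptide. SAP 2.1.3 takes fasting proinsulin and C-peptide from the pre-meal sample, so those endpoints depend on the same subset. SAP 2.5.4 allocates discontinuation, pre-rescue and early end-of-treatment values to a visit by study day (day 161 onward becomes Week 26) and then imputes visits still empty.

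**The concern.** Membership depends on something measured after randomization, and in the normal course that measurement is the endpoint itself. A consenting patient who had the Visit 3 test and then left without another meal test never enters the set. That is the patient for whom control-based imputation was specified: the outcome is missing, and the plan wants it filled with placebo-like values.

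The rule also separates patients who differ only in whether an exit test was obtained. A dropout tested before study day 161 qualifies through that value, has no Week 26 value after allocation, and is imputed. A dropout without such a test is removed. Under the plan's own assumption, removing these patients moves the estimated effect away from zero, in a subset small enough for a few exclusions to matter.

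**Working it through.** **Plan's own figures.** The documents size no meal-test endpoint and give no dropout rate. The only power figure is for HbA1c (Protocol 11.1): 60 versus 30 patients, difference 0.7%, SD 1.1%, two-sided 5%. It reproduces: 0.7/[1.1 × √(1/60 + 1/30)] = 2.85, giving 81.2% power by the normal approximation and 80.4% by noncentral t, against the stated 80%. Nothing below depends on it.

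**Inputs.**

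- Substudy size: up to 50% of patients (Protocol 9.2.1.2.2). If uptake is balanced across arms (an assumption), that is at most 0.5 × 60 = 30 per dose and 0.5 × 30 = 15 on pooled placebo.
- d: share of consenting patients in an active arm with no Week 26 meal test. Assumed, 5% to 30%.
- q: share of those who have an early meal test and so meet the SAP 2.3.7 rule. Assumed, 0 to 1.
- Missing active-arm patients have placebo-like values, so their mean difference from placebo is zero. This follows the plan's imputation assumption. It is a simplification: if an early value enters the imputation model, the difference need not be exactly zero.

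**Formulas**, with the effect among patients who have a Week 26 test set to 1:

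- All consenters kept and imputed: effect = 1 - d.
- SAP 2.3.7 set: share kept = (1 - d) + dq, and effect = (1 - d)/[(1 - d) + dq].
- Overstatement factor (second divided by first) = 1/[(1 - d) + dq].

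| d | q = 0 | q = 0.5 | q = 1 |
|---|---|---|---|
| 5% | 1.05 | 1.03 | 1.00 |
| 10% | 1.11 | 1.05 | 1.00 |
| 20% | 1.25 | 1.11 | 1.00 |
| 30% | 1.43 | 1.18 | 1.00 |

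For d = 20%: 1/0.80 = 1.25 at q = 0; 1/(0.80 + 0.10) = 1.11 at q = 0.5; 1/(0.80 + 0.20) = 1.00 at q = 1.

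**Numbers left** at d = 20%, with the same d and q on placebo: 24 per dose and 12 on placebo at q = 0; 27 and 13.5 at q = 0.5; 30 and 15 at q = 1.

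**The case against.** **The SAP does not say that the meal-test ANCOVA uses this set.** That is correct. ITT is the default, and in the text available the substudy set is only defined and counted. SAP Appendix B, a summary of the analyses, is listed in the contents but was not available and may settle it. Against this, literal ITT would mean imputing meal tests for at least half the trial, who never had one even at baseline. SAP 2.3.4 to 2.3.6 each state ITT, and 2.3.7 does not. So 2.3.7 is the likely set, but this is inference. If another set is meant, the text still has to say so.

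**A reader might infer that this is a completers set, with almost nothing left to impute.** The documents do not support that. Patients who stop IMP but stay in the study are retested at Week 26, off drug. Rescued patients are tested before rescue and again at the end. Some dropouts have an exit test that keeps them in. Selection is on having a meal test, not on tolerating treatment. Selection that differs by dose is conceivable, but nothing in the documents quantifies it.

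**A reader might extend the point to Holter and VAS.** The imputation argument does not reach them. Holter heart rate is a safety variable with a Week 14 recording as well, summarised descriptively on the safety population (SAP 2.1.4.8, 2.4.5, 2.4.5.7). VAS is a pharmacodynamic biomarker, assigned to ITT and summarised descriptively (SAP 2.1.6, 2.3.4, 2.4.7).

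**The stakes are limited.** These are secondary endpoints outside the hierarchy (SAP 2.4.4.3), in an opt-in subset of a Phase 2 trial. That stands, and it sets the severity.

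**Conclusion.** The point holds for meal-test glucose, insulin, proinsulin and C-peptide, and for fasting proinsulin and C-peptide. SAP 2.3.7 selects on a post-randomization value, excludes dropouts without an early meal test, and is not reconciled with the imputation in 2.4.4.2 and 2.5.4.

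At an assumed 20% without a Week 26 test, the overstatement runs from 0% (every such patient has an early test) through 11% (half do) to 25% (none do). The last is a worst case, not an expected value. These figures rest on the assumed d and q, on placebo-like missing outcomes, and on 2.3.7 being the set actually used. Under those assumptions the factor is never below 1, so any bias enlarges the apparent effect. Severity is minor to moderate.

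**What to change.** 1. In SAP 2.3.7, define the meal-test set as all randomized patients with substudy consent and a Visit 3 meal test, analysed as randomized. Delete the post-baseline condition for this set. Visit 3 precedes randomization, so requiring that test introduces no post-randomization selection.
2. In SAP 2.4.4.2, name this set for the meal-test efficacy endpoints and for fasting proinsulin and C-peptide. Impute every missing Week 26 value as in 2.4.4.1.
3. State how the imputation uses early meal-test values that 2.5.4 allocates to visits at which no meal test is scheduled.
4. Keep the set with observed values as a sensitivity analysis.
5. Leave Holter and VAS out of the imputation.
6. Reconcile footnote a of Protocol 1.2 with Protocol 9.2.1.2.2, which state the meal test at IMP discontinuation differently.

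The cost is a few lines in the SAP plus the protocol reconciliation. Expect slightly less favourable estimates and somewhat wider intervals.

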#### **Meal test related variables are:**

- PPG and in blood glucose excursion in response to a standardized meal test in up to 50% subset of all patients from baseline to Week 26 at time points premeal, 10min, 20min, 0.5h, 1h, 1.5h, 2h, 3h, 4h post meal,
- Insulin, proinsulin, and C-peptide and associated excursion values in response to a standardized meal test in up to 50% subset of all patients from baseline to Week 26 at time points premeal, 10min, 20min, 0.5h, 1h, 1.5h, 2h, 3h, 4h post meal,
- VAS for appetite/satiety score in response to a standardized meal test in up to 50% subset of all patients from baseline to Week 26 at time points premeal, 4 hours post meal.

#### **Holter monitor related variables are**

- Twenty-four hour average heart rate,
- Night time average heart rate.

## 2.4 STATISTICAL METHODS

### 2.4.1 Demographics and baseline characteristics

Continuous data will be summarized by treatment group using the number of available observations (N), mean, standard deviation (SD), minimum, median, and maximum. Categorical and ordinal data will be summarized using counts and percentages in each treatment group.

Parameters will be summarized based on the randomized population analyzed in the treatment group to which they were randomized. Analyses for the safety population will be included in the appendices if the size of the safety population is different (>10%) from the size of that in the primary analysis population (ie, randomized patients) for any treatment group.

Parameters described in [Section 2.1.1](#) will be summarized by treatment group and overall (pooled across treatment groups) using descriptive statistics.

P-values on the treatment difference for the demographic and baseline characteristic data will not be calculated.

In general, no specific description of the safety parameters will be provided at baseline. If relevant, the baseline values will be described along with each safety analysis.

In general, no specific description of the efficacy parameters will be provided at baseline. If relevant, the baseline values will be described along with each efficacy analysis.

### 2.4.2 Prior or concomitant medications

The prior, concomitant and posttreatment medications will be presented in the randomized population for each treatment group (and overall for the summary of prior medications), using counts and percentages. No statistical test for the between-group difference will be performed.

Medications will be summarized by treatment group according to the WHO-DD dictionary, considering the first digit of the anatomic category (ATC) class (anatomic category) and the first 3 digits of the ATC class (therapeutic category). A given medication may be classified in more than 1 ATC class. All ATC codes corresponding to a medication will be summarized, and a patient will be counted once in each ATC category (anatomic or therapeutic) linked to the medication. Therefore a patient may be counted several times for the same medication.

Prior medications will be presented by anatomic and therapeutic categories and sorted by decreasing frequency of ATC based on the overall incidence across treatment groups. In case of equal frequency regarding ATCs (anatomic or therapeutic categories), alphabetical order will be used.

Concomitant and posttreatment medications will be presented by anatomic and therapeutic categories and sorted by decreasing frequency of ATC based on the incidence in the SAR425899 0.20 mg dose group. In case of equal frequency regarding ATCs (anatomic or therapeutic categories), alphabetical order will be used.

### **2.4.3 Extent of investigational medicinal product exposure and compliance**

The extent of IMP exposure and compliance will be assessed and summarized by actual treatment received within the safety population ([Section 2.3.2](#)).

#### **2.4.3.1 Extent of investigational medicinal product exposure**

The extent of IMP exposure will be assessed by the duration of IMP exposure.

The duration of IMP exposure is defined as last dose date of double-blind IMP – first dose date of double-blind IMP + 1 day, regardless of unplanned intermittent discontinuations (see [Section 2.5.3](#) for calculation in case of missing or incomplete data).

Duration of IMP exposure (days) will be summarized descriptively as a quantitative variable (number of patients exposed, mean, SD, minimum, median, and maximum). In addition, duration of treatment exposure will also be summarized categorically by numbers and percentages for each of the following categories and cumulatively according to these categories:

- 1 to 14 days,
- 15 to 28 days,
- 29 to 56 days,
- 57 to 98 days,
- 99 to 182 days,
- >182 days.

Additionally, the cumulative duration of treatment exposure will be provided, defined as the sum of the duration of treatment exposure for all patients, and will be expressed in patient years.

#### **2.4.3.2 Compliance**

A given administration will be considered noncompliant if the patient did not take the planned dose of treatment as required by the protocol. No imputation will be made for patients with missing or incomplete data.

Percentage of compliance for a patient will be defined as the number of days that the patient was compliant divided by the total number of days that the patient was planned to take during the treatment epoch defined in [Section 2.1.4](#) (ie, from the first date to the last date of double-blind IMP administration).

Above-planned dosing percentage for a patient will be defined as the number of days that the patient took a higher dose than planned divided by the total number of days that the patient was planned to take during the treatment epoch.

Under-planned dosing percentage for a patient will be defined as the number of days that the patient took a lower dose than planned divided by the total number of days that the patient was planned to take during the treatment epoch.

Treatment compliance, above-planned, and under-planned dosing percentages will be summarized descriptively as quantitative variables (number, mean, SD, median, minimum, and maximum). The percentage of patients whose compliance is <80% will be summarized. In addition, numbers and percentages of patients with at least 1 above-planned dose administration will be provided, as well as numbers and percentages of patients with 0, (0, 20%], and >20% under-planned dose administrations.

The planned dose is defined to be the intended dose as collected in the eCRF.

Cases of overdose (see study protocol for further details) will constitute AEs and be analyzed as such. More generally, dosing irregularities related to randomization procedure will be listed in [Section 2.2.1](#).

#### **2.4.4 Analyses of efficacy endpoints**

Efficacy analyses will be performed on the ITT population using efficacy assessment collected during the study, including those obtained after IMP discontinuation or introduction of rescue therapy, unless otherwise specified.

Unscheduled post-baseline measurements will be allocated to a post-baseline visit according to the criteria described in [Section 2.5.4](#)

##### **2.4.4.1 Analysis of primary efficacy endpoint(s)**

The statistical test will be 2-sided tests at a nominal 5% significance level.

##### ***Primary analysis***

The primary efficacy endpoint of change in HbA1c from baseline to Week 26 will be analyzed with missing post-baseline values imputed by placebo control-based multiple imputation (MI) method under the missing not at random framework (5, 6, 7).

- For placebo group patients, missing data will be imputed based on the placebo group data.
- For patients in the SAR425899 dose groups and liraglutide group, missing data will be imputed as if the patients were on placebo group throughout the study.

For missing HbA1c value at baseline, missing data will be imputed using MI under the missing at random (MAR) assumption. Missing data at baseline will be imputed using regression method that includes randomization stratum of screening HbA1c ( $\leq 8.0\%$ ,  $> 8.0\%$ ), randomization stratum of Visit 4 (Day 1) BMI ( $< 35.0 \text{ kg/m}^2$ ,  $\geq 35.0 \text{ kg/m}^2$ ), and baseline value in the imputation model (see sample code Part 1c in [Appendix D](#)).

The change from baseline at Week 26 values will be derived from observed or imputed Week 26 HbA1c values (see sample code Part 1a in [Appendix D](#)). Each of the complete dataset will be analyzed by the Analysis of Covariance (ANCOVA) model with treatment groups (SAR425899 0.12 mg, SAR425899 0.16 mg, SAR425899 0.20 mg, placebo and liraglutide), randomization strata of screening HbA1c value ( $< 8\%$ ,  $\geq 8\%$ ), randomization strata of Visit 4 (Day 1) BMI

(<35.0 kg/m^2, ≥35.0 kg/m^2), and country as fixed effects, and baseline HbA1c value as a covariate (see sample code Part 2 in [Appendix D](#)).

Results from each complete dataset will be combined using Rubin's rule to provide the following. Three trend tests are planned on HbA1c. First trend test will be performed to test the hypothesis that HbA1c reduction from baseline at Week 26 increases with increase in dose. The test will be based on a contrast under the ANCOVA framework and with coefficients of +3, +1, -1, -3 and 0 for SAR425899 0.20 mg, SAR425899 0.16 mg, SAR425899 0.12 mg, placebo and liraglutide, respectively. The second trend test (SAR425899 0.16 mg versus placebo) is performed with coefficients of 0, +1, 0, -1 and 0 for SAR425899 0.20 mg, SAR425899 0.16 mg, SAR425899 0.12 mg, placebo and liraglutide, respectively. The third trend test (SAR425899 0.12 mg versus placebo) is performed with coefficients of 0, 0, 1, -1 and 0 for SAR425899 0.20 mg, SAR425899 0.16 mg, SAR425899 0.12 mg, placebo and liraglutide, respectively. Adjusted mean change in HbA1c from baseline to Week 26 for each treatment group, as well as the between-group difference (comparing each SAR425899 dose group versus placebo) and the 95% confidence interval (CI) for the between-group difference will also be provided. The overall Type 1 error for multiple comparisons of the HbA1c and body weight will be controlled by a Hierarchical testing procedure as detailed in [Section 2.4.4.3](#).

The ANCOVA model will be implemented using statistical analysis system (SAS®) (Version 9.4 or higher) MIXED procedure (PROC MIXED).

